1.1 Background and rationale

The administration of oxygen is a fundamental part of care in paediatric critical illness with supplemental oxygen offered to nearly every acutely unwell child. However, the optimal targets for systemic oxygenation are unknown. Observational data suggest harm from too generous use of supplemental oxygen in adults and children. However currently, there is no high-quality evidence from randomised controlled trial (RCT) data to support this practice and guide clinicians' use of oxygen. Therefore the OXY-PICU trial has been designed to determine whether a conservative target of peripheral oxygen saturation of 88-92% has better clinical outcomes than a more liberal target of >94%.

This document describes the proposed Statistical Analyses Plan (SAP) for the trial. The SAP is agreed in advance of inspecting the outcome data for the trial, so that data-derived decisions in the analyses are avoided. This SAP has been prepared in accordance with published guidelines¹.

1.2 Aim and Objectives

The overall aim of Oxy-PICU is to determine if the risks of interventions employed on intensive care to raise peripheral oxygen saturation to >94% exceed their benefits when compared to a peripheral oxygen saturation of 88-92%.

1.2.1 Primary Objectives

- Composite outcome of mortality and duration of organ support at 30 days (rank-based analysis with death ranked as worse than 30 days of organ support)
- Incremental costs, quality-adjusted life years (QALYs) and net monetary benefit at 12 months

1.2.2 Secondary Objectives

- Incremental costs at 30 days
- Mortality at PICU discharge, 30 days, 90 days and 12 months
- Time to liberation from ventilation
- Duration of organ support
- Length of PICU and hospital stay
- Functional status at PICU discharge
- Health-related quality of life (HrQoL) at 12 months

2 Study Methods

2.1 Trial design

Oxy-PICU is a pragmatic, open, multiple centre parallel group randomised controlled trial with integrated economic evaluation in infants and children accepted for unplanned admission to a participating PICU.

2.2 Randomisation

Patients will be randomised on a 1:1 basis to either a liberal (>94%) or conservative (88-92%) SpO2 target, using minimisation to balance the arms with respect to age (<12 months / \geq 12 months); site; primary reason for admission (lower respiratory tract infection vs. Other); and severity of abnormality of gas exchange: SF ratio <221 with PEEP \geq 5 vs. Other.

2.3 Sample size

The primary clinical outcome will be analysed using rank-based methods, with death at 30 days ranked as the worst outcome. To achieve 90% power, using simulations based on data from the Oxy-PICU pilot RCT, to detect a clinically meaningful reduction in the mean duration of organ support of 12 hours from 120 to 108 hours and assuming no impact on 7.5% mortality requires a total sample size of 2040 patients (allowing for withdrawal/refusal of deferred consent of 10%).

2.4 Framework

The primary clinical outcome, and specified secondary outcomes will be tested for superiority.

2.5 Analysis of internal pilot

The internal pilot phase was evaluated 6 months after the first site has opened to recruitment. At this point the following key progression criteria were assessed and classified as green, amber or red:

	Green	Amber	Red
Number of sites open to recruitment	≥10	6-9	<6
Recruitment rate (per	≥4.5	3-4.5	<3
site per month)	(≥75% of anticipated)	(40-75% of anticipated)	(<40% of anticipated)
Separation in mean measurements between groups	SpO₂: ≥3% OR FiO₂ concentration: ≥0.1	SpO ₂ : 1.5-3% OR FiO ₂ concentration: 0.05 – 0.09	SpO ₂ : <1.5% OR FiO ₂ concentration: <0.05
Treatment adherence – carried out per protocol	≥75% cases	50-75% cases	<50% cases

Mean measurements of SpO2 and FiO2 were calculated using all available post-randomisation recorded values for all randomised patients while remaining on invasive ventilation.

Treatment adherence was calculated as the percentage of patients classified as adherent, divided by the total number of randomised patients. A patient was defined as adherent if no potential deviations have been recorded in the first seven days of treatment, where a deviation is classified as either of the following:

- at least four consecutive hourly measurements (constituting three consecutive hours) where the SpO2 is below the target range and both the FiO2 and MAP has stayed constant (or decreased) over all four observations.
- at least four consecutive hourly measurements (constituting three consecutive hours) where the SpO2 is above the target range and the FiO2 and/or MAP (if >16) has stayed constant (or increased) over all four observations.

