3.2 Adherence and protocol deviations

3.2.1 Exposure

Exposure to the intervention will be assessed by the following parameters, which will be calculated for each treatment group and summarised using descriptive statistics (mean, standard deviation, median and interquartile range (IQR), or counts and percentages for binary and categorical variables) unless otherwise specified:

- SpO2 recorded while on invasive ventilation
- SpO2 recorded while on invasive ventilation with supplemental oxygen (FiO2 >0.21)
- FiO2 recorded while on invasive ventilation
- Hours of invasive ventilation within the following categories: SpO2 >92% with FiO2=0.21; SpO2 >92% with FiO2 >0.21; SpO2 88-92%; SpO2 <88%, both overall and as a percentage of total hours of ventilation.

Further treatment patterns across each group will be explored using summary statistics and graphic methods only, no formal statistical testing will be performed.

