3.2.2 Protocol adherence

The number and % of patients with at least one potential protocol deviation (as defined previously in section 2.5) will be reported, and the total number of such deviations.

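### The above-range deviation rule counts conservative-arm children above 92% on room air with MAP at or below 16, although it leaves no setting to reduce

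*SAP*

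**What the plan says.** Section 2.2 sets the two targets: "Patients will be randomised on a 1:1 basis to either a liberal (>94%) or conservative (88-92%) SpO2 target". The conservative range has a lower and an upper limit; the liberal target has only a lower one.

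Section 2.5 defines two kinds of deviation, each needing at least four consecutive hourly readings:

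- Above range: "SpO2 is above the target range and the FiO2 and/or MAP (if >16) has stayed constant (or increased") across all four readings.
- Below range: "SpO2 is below the target range and both the FiO2 and MAP has stayed constant (or decreased) over all four observations".

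One episode is enough to make a child non-adherent: "A patient was defined as adherent if no potential deviations have been recorded in the first seven days of treatment". For the pilot, adherence was the "percentage of patients classified as adherent, divided by the total number of randomised patients", so the arms were pooled.

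Section 3.2.2 carries the definition into the final report: the number and percentage of patients with "at least one potential protocol deviation (as defined previously in section 2.5) will be reported", together with the total number of deviations. It does not say that the counts will be given by arm, or that above-range and below-range events will be kept apart.

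Section 3.2.1 divides ventilated hours into "SpO2 >92% with FiO2=0.21; SpO2 >92% with FiO2 >0.21; SpO2 88-92%; SpO2 <88"%, so the SAP expects some children to be above 92% on room air and gives that state its own category.

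**The concern.** The above-range criterion is meant to pick up a child who stays above target while support is not reduced. On room air that reasoning fails. FiO2 of 0.21 is constant because it cannot be lowered, and the rule brings MAP in only when it exceeds 16. A child with FiO2 0.21 and MAP at or below 16 meets the definition whatever the clinical team does within its terms. Section 3.2.1 draws the distinction that section 2.5 omits.

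The artefact is one-sided, because a target of >94% cannot be exceeded. In an open trial of two oxygenation targets, the adherence table helps a reader judge whether a null result reflects no effect or poor delivery. Here it would make delivery look worse in one arm for a reason unrelated to delivery.

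A second defect is that the and/or in the above-range criterion can be programmed in two ways that give different counts, whereas the below-range criterion says plainly that both settings must be unchanged or lower.

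**Working it through.** The SAP states no adherence figure, so there is none to reproduce. The check applies the rule as written to example patterns and then shows how the result scales under labelled assumptions.

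**Step 1. The rule applied to four consecutive hourly readings.** Above range means SpO2 above 92% in the conservative arm and is impossible in the liberal arm (section 2.2). The and/or is read first as OR (either setting constant or rising is enough) and then as AND (every applicable setting must be constant or rising). MAP applies only if above 16. SpO2 is 97% in every row.

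| Pattern | Conservative, OR | Conservative, AND | Liberal |
|---|---|---|---|
| FiO2 0.21, MAP constant at 10 | flagged | flagged | never |
| FiO2 0.21, MAP falling from 10 to 8 | flagged | flagged | never |
| FiO2 0.21, MAP constant at 18 | flagged | flagged | never |
| FiO2 0.21, MAP falling from 20 to 17 | flagged | not flagged | never |
| FiO2 falling from 0.6 to 0.3, MAP constant at 18 | flagged | not flagged | never |
| FiO2 falling from 0.6 to 0.3, MAP constant at 12 | not flagged | not flagged | never |

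The first two rows are the core of the point. The flag arises under either reading, and neither setting offers a way to avoid it. In the third row the rule treats MAP as something that could have been reduced, so that flag is not plainly false. The fourth and fifth rows show that the meaning of and/or changes the count.

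**Step 2. The below-range rule.** With SpO2 85%, FiO2 1.0 and MAP constant at 20, the child is flagged in both arms. With MAP rising, the child is flagged in neither. Below-range deviations are therefore possible in either arm.

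**Step 3. How the artefact would scale.** Let *a* be true adherence, taken as equal in both arms, and *f* the share of otherwise adherent conservative-arm children flagged only through the artefact. Both are assumptions; the SAP gives neither.

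- Conservative arm reads a × (1 − f).
- Liberal arm reads a.
- Pooled at 1:1: [a + a(1 − f)] / 2 = a(1 − f/2).

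With a = 80%:

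| f | Conservative arm | Liberal arm | Pooled |
|---|---|---|---|
| 5% | 0.80 × 0.95 = 76% | 80% | 78% |
| 10% | 0.80 × 0.90 = 72% | 80% | 76% |
| 20% | 0.80 × 0.80 = 64% | 80% | 72% |
| 30% | 0.80 × 0.70 = 56% | 80% | 68% |

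Pooled adherence falls below the 75% green limit of section 2.5 once f exceeds 2(1 − 0.75/a). That is 12.5% for a = 80%, 23.5% for a = 85% and 33.3% for a = 90%.

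**Step 4. Where the rule is used.** It enters the pilot progression criterion (2.5) and the adherence report (3.2.2). The per-protocol population in section 3.3 is defined by eligibility breaches and by a clinical decision, recorded immediately after randomisation, not to follow the trial treatment. It does not use this rule. No planned test or model does either.

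**The case against.** The strongest reply is that little depends on this count. The pilot decision has been taken and pooled the arms, which halves any effect. Separation is measured by SpO2 and FiO2 directly, summarised by arm in section 3.2.1. The same section gives hours above 92% on room air by arm, so a careful reader could discount the deviation count. The SAP also calls these deviations potential. All of this limits the consequence. It does not correct the count: hours on room air cannot be turned into a number of children wrongly flagged, and no review step is described between a potential deviation and its being counted.

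The wording may also follow a treatment algorithm in the protocol, which is not at hand. That is a fair reason not to call either reading of and/or wrong, and not to exempt every reading at FiO2 0.21, since the rule treats MAP above 16 as a second setting.

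A reader might go further in four ways that the SAP does not support:

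- *Children whose oxygen is being weaned are flagged in general.* This happens only when MAP is above 16 and not falling, and only under the OR reading.
- *Non-adherence as a whole is inflated in one arm only.* The one-sidedness belongs to the above-range criterion. Below-range flags can arise in both arms, including in a child whose FiO2 is already 1.0, although there MAP could still rise.
- *The inflation can be put at tens of percentage points.* The SAP gives no count of children ventilated on room air above 92%, and some of them will also have genuine deviations.
- *The lack of a 94% cut in the exposure categories is an error.* It is a reporting preference; SpO2 is also summarised by mean, SD, median and IQR in each arm.

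**Conclusion.** The point holds in a limited form. As written, the above-range criterion counts a conservative-arm child on room air above 92% with MAP at or below 16 as a deviation, although the rule leaves nothing to reduce. This conflicts with the distinction made in section 3.2.1. Because the liberal target has no upper limit, these flags fall only in the conservative arm, and that arm's reported adherence is understated.

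The size cannot be computed from the SAP. The figures above rest on assumed values of true adherence and of the share affected, and on equal true adherence in the two arms; they show scale only. The effect is confined to the descriptive adherence report and to the pilot criterion already assessed. The primary, ITT and per-protocol analyses are untouched. The correction is still worth making, because a stated rule gives a wrong, one-sided count that can be put right cheaply before the table is produced.

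**What to change.** For the section 3.2.2 report:

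1. Do not count above-range runs in which FiO2 is 0.21 and MAP is not above 16 throughout. This is consistent with the room-air category in section 3.2.1 and leaves in place the rule's treatment of MAP above 16.
2. State whether the and/or in the above-range criterion means AND or OR, reconciled with the treatment algorithm and with the wording of the below-range criterion.
3. Report the number and percentage of patients with a deviation, and the total number of deviations, by arm and separately for above and below range.

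The cost is a change of SAP wording and a small recoding of hourly SpO2, FiO2 and MAP values already collected under section 2.8. The downside is that the final definition would differ from the one used in the pilot. Showing the adherence figures under both definitions deals with that.

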2.6 Statistical interim analysis and stopping criteria

A single interim analysis will be carried out, after recruitment and follow-up to day 30 of the first 1020 patients. At this point, the primary clinical endpoint will be compared between arms, with early termination of the trial recommended if either arm is shown to be superior with p<0.001 (Peto-Haybittle stopping rule).

2.7 Timing of final analysis

The trial database will be locked and the main analysis of the trial will be performed after all patients randomised to the trial have reached their 30 day follow-up timepoint, with one further update of long term outcomes only planned once all patients have reached their 12 month follow-up timepoint.

2.8 Timing of outcome assessments

Following randomisation, observations are recorded hourly on the hour (+/-15 minutes) for 7 days (or until PICU discharge if earlier) and include receipt of invasive ventilation (yes/no) and, where children are on invasive ventilation, SpO2, mean airway pressure (MAP), and FiO2. For days 8 onwards (or until PICU discharge if earlier), the same observations are recorded twice daily at 09:00 and 21:00 (+/- 1 hour).

Receipt of any other type of organ support (yes/no) is recorded once daily until day 30 or PICU discharge.

Other outcomes are collected at discharge from critical care (date/time of liberation from ventilation, survival status at PICU discharge and discharge method, and functional status as measured using the Paediatric Cerebral Performance Category (PCPC) and Paediatric Overall

performance Category (POPC)), and at ultimate discharge from acute hospital (survival status at hospital and ultimate PICU discharge, locations of care after PICU discharge).

Specified adverse events and serious adverse events are collected from randomisation until 30 days after randomisation or discharge from PICU, whichever is later.

Long term survival is collected at 12 months, using either linkage to national survival data (NHS Digital) or by local research teams. Once 12 month survival status is known, PEDS-QL and CHU-9D quality of life questionnaire will be emailed or posted to consenting parents/legal guardians.

3 Statistical Principles

3.1 Confidence intervals and p-values

The primary clinical outcome will be tested for superiority. Other secondary outcomes will be tested for superiority, where testing is specified, or summarised and reported using descriptive statistics. Statistical tests will be two-sided with significance set at P<0.05 unless otherwise specified. Effect estimates will be reported with 95% confidence intervals. There will be no adjustment for multiple testing. The results of subgroup analyses will be interpreted taking into account accepted criteria for credible subgroup effects²,³.

3.2 Adherence and protocol deviations

3.2.1 Exposure

Exposure to the intervention will be assessed by the following parameters, which will be calculated for each treatment group and summarised using descriptive statistics (mean, standard deviation, median and interquartile range (IQR), or counts and percentages for binary and categorical variables) unless otherwise specified:

- SpO2 recorded while on invasive ventilation
- SpO2 recorded while on invasive ventilation with supplemental oxygen (FiO2 >0.21)
- FiO2 recorded while on invasive ventilation
- Hours of invasive ventilation within the following categories: SpO2 >92% with FiO2=0.21; SpO2 >92% with FiO2 >0.21; SpO2 88-92%; SpO2 <88%, both overall and as a percentage of total hours of ventilation.

Further treatment patterns across each group will be explored using summary statistics and graphic methods only, no formal statistical testing will be performed.

3.2.2 Protocol adherence

The number and % of patients with at least one potential protocol deviation (as defined previously in section 2.5) will be reported, and the total number of such deviations.

3.3 Analysis Population

Following the intention to treat (ITT) principle, all randomised patients will be included in the analysis of the primary clinical endpoint, excluding only those where consent to access medical records was withheld or unobtainable (or were lost to follow-up before PICU discharge for any other reasons) before 30 days post randomisation.

A sensitivity analysis will be conducted in the per-protocol (PP) population, consisting of all randomised patients excluding those who were found to have breached the eligibility criteria following randomisation, and those where a clinical decision not to follow the trial treatment was recorded immediately post randomisation.

4 Trial population

4.1 Screening data

Screening logs will be used to record all patients who are admitted or accepted for admittance to critical care. The following summary measures will be reported:

- Number and % of patients who did not meet inclusion criteria, overall and by criteria
- Of the patients who met the inclusion criteria, number and % who met exclusion criteria, overall and by criteria.
- Of the eligible patients (i.e. met inclusion criteria and did not meet exclusion criteria), number and % not randomised, overall and by reason (if known)

4.2 Eligibility

4.2.1 Inclusion Criteria

- Less than 16 years and more than 38 weeks corrected gestational age
- Enrolled within six hours of first meeting all the following criteria;
 - Accepted to a participating PICU as an unplanned admission

- Receiving invasive mechanical ventilation with supplemental oxygen for abnormal gas exchange

- Face-to-face contact with PICU staff or transport team

4.2.2 Exclusion Criteria

- Not expected to survive to ICU admission
- Brain pathology/injury as primary reason for admission (e.g. traumatic brain injury, post-cardiac arrest, stroke, convulsive status epilepticus without aspiration)
- Known pulmonary hypertension
- Known or suspected sickle cell disease
- Known or suspected uncorrected congenital cardiac disease
- End-of-life care plan in place with limitation of resuscitation
- Receiving long-term invasive mechanical ventilation prior to this admission
- Recruited to Oxy-PICU in a previous admission

4.3 Recruitment

A CONSORT flow diagram will be completed to describe number of patients randomised and availability of primary clinical endpoint and 12 month follow-up data within each arm.

4.4 Consent

The parent/legal guardian of trial participants will be asked to consent to the study as soon appropriate and practical after randomisation (usually within 24-48 hrs of randomisation but the timing will vary according to the child's clinical situation). They may consent to any one or more of the following aspects: Trial continuation (i.e. treatment); access to medical records for ongoing data collection; completion of the parental stress questionnaire (at/around the time of consent); to receive a follow-up questionnaire at 6 months post-randomisation; sharing of anonymised data to support future research; to be contacted regarding future research participation. When consent is refused for access to medical records (regardless of whether or not consent has been given for trial continuation), all trial data collection should cease and no data linkage to PICANET or NHSDigital should be performed. Data collected by site staff directly to the trial CRF up to the point of consent refusal will be retained and used for analysis, but no events after this point will be recorded or reported on. If any data has already been obtained via linkage from PICANET or NHSDigital, this data will be deleted.

Where consent has been refused for trial continuation, but granted for access to medical records, data collection and linkage may continue and the patient may be included in the analysis as appropriate for each endpoint.

If consent is refused for access to medical records and/or trial continuation, the parental stress questionnaire may still be completed and reported on if this has been consented to.

4.5 Withdrawal/follow-up

Once given, consent can be withdrawn at any time up to the end of the study. Data collected up to the point of non-consent or withdrawal of consent to data collection will be retained.

4.6 Baseline patient characteristics

Baseline data is collected at critical care admission via data linkage to PICANET, and directly via trial CRF for physiology at randomisation. The following baseline demographic and clinical data will be summarised in the ITT population, by allocated treatment group, (using mean, standard deviation,

median and interquartile range (IQR), or counts and percentages for binary and categorical variables), but not subjected to statistical testing:

Age (years) – median and IQR, and number and % by age group (<=12 months, >12 months))

Ethnic group

Sex (male, female) – number and %

Arterial PaO2, base excess, lactate, systolic blood pressure, and mean airway pressure at randomisation – median and IQR, mean and SD

Comorbidities - number and % by type of comorbidities (as specified on the CRF)

Main reason for PICU admission (from PICANET linkage)

5 Analysis

